5.3 ELOTUZUMAB ADMINISTRATION

TABLE 10. Product information table – product description

Product description and dosage form	Potency	Primary packaging (volume)/label type	Appearance	Storage conditions (per label)
Elotuzumab powder for solution for infusion	300mg /vial or 400 mg/vial	20 ml vial /Open label	Sterile white to off-white, preservative-free, lyophilized cake	Store at 2°C –8°C Protect from light. Do not freeze or shake

Administration and handling of elotuzumab (See also Appendix 6)

The lyophilized elotuzumab drug product should be stored at 2°C to 8°C. Prior to administration the drug must be reconstituted with sterile water for injection, then further diluted in 0.9% sodium chloride normal saline. After the dose is diluted in normal saline, the elotuzumab infusion must be administered within 8 hours if stored at room temperature. If a delay is anticipated, the prepared dose may be refrigerated at 2°C to 8°C for up to 24 hours. If stored under refrigerated conditions, the prepared study drug solution should be equilibrated to room temperature (this takes 2-2.5 hours) and the container must be gently inverted to mix well before administration. Do not use the accelerated warming methods. If administration is delayed beyond the specified time, the prepared dose solution must be discarded, and the reason documented. The dose of elotuzumab to be given to a study patient will be calculated by multiplying the patient's weight (kg) by 10 mg/kg.

Premedication before elotuzumab

Dexamethasone

On weeks without elotuzumab, administer the weekly dose of 40 mg dexamethasone orally on day 1, 8, 15, and 22 (-1 to +3 days). At the investigator's discretion, the oral dexamethasone may be given as a split dose over 2 consecutive days each week.

On weeks of elotuzumab infusion, split the weekly dose of dexamethasone between oral and IV administration as indicated below under "Premedication Before Elotuzumab"

At the discretion of the investigator, the oral dexamethasone component may be given as a split dose 12 – 24 hours and 3 hours prior to elotuzumab

Premedication before elotuzumab

1. Dexamethasone 28 mg po (between 3 - 24 hours prior to the start of elotuzumab infusion or as a split dose 12 – 24 hours and 3 hours prior to elotuzumab) and
2. Dexamethasone 12 mg IV (on the day of elotuzumab infusion 45-90 minutes prior to the start of infusion).
3. H1 blocker: diphenhydramine (25 - 50 mg po or IV) or equivalent (45-90 minutes prior to the start of infusion)
4. H2 blocker: ranitidine (50 mg IV) or equivalent (45-90 minutes prior to the start of infusion)
5. Paracetamol 500 – 1000 mg (Acetaminophen SIC! Not used in Nordic countries (650 - 1000 mg po), (45-90 minutes prior to the start of infusion)

Premedication regimen in patients with a prior infusion reaction

Subjects with prior infusion reaction must receive H1, H2 blockers and paracetamol (acetaminophen) at maximum doses specified above.

In addition, dexamethasone premedication should be administered as per the Table 11 below:

Table 11. Corticosteroid Premedication

Prior infusion reaction	Corticosteroid premedication prior to elotuzumab
-------------------------	--

Table 11. Corticosteroid Premedication

Prior infusion reaction	Corticosteroid premedication prior to elotuzumab
None or only grade 1 infusion reaction	28 mg PO dexamethasone (3 - 24 hrs prior to elotuzumab) AND 12 mg IV dexamethasone at least 45-90 min prior to elotuzumab
Prior grade 2 infusion reaction	28 mg PO dexamethasone (3 - 24 hrs prior to elotuzumab) AND 14 mg IV dexamethasone at least 45-90 min prior to elotuzumab
Prior grade 3 or recurrent grade 2 infusion reaction	8 mg oral dexamethasone (12 - 24 hrs prior to elotuzumab) AND 8 mg oral dexamethasone (at least 3 hrs prior to elotuzumab) AND 18 mg IV dexamethasone at least 45-90 min prior to elotuzumab

At the discretion of the investigator, the 28mg oral dexamethasone component may be given as a split dose: 12mg PO (12 – 24 hours prior to elotuzumab) AND 16mg PO (3 hours prior to elotuzumab).

If a subject with a prior grade 2 - 3 infusion reaction also requires dose reduction of dexamethasone, the weekly dexamethasone on the days of elotuzumab infusion should be no lower than 8 mg IV (on the day of elotuzumab infusion at least 45 minutes prior to elotuzumab).

Subjects with a grade 4 elotuzumab infusion reaction must have elotuzumab permanently discontinued.

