This Nordic Myeloma Study Group study is a phase 2 study for advanced MM patients below 75 years of age. The main aim of this study is to assess the ORR with a new drug combination, carfilzomib + elotuzumab + dexamethasone (CAR-ELO-Dex). Even if this is not a randomized study rough comparisons can be done with earlier reports of different regimens in the same clinical situation. In addition, safety assessment is of critical importance for a new regimen. A modern concept is to study the depth of CR responses with a sensitive multiparameter flow cytometry (MFC) method for MRD assessment – an endpoint that is mostly lacking in previous studies for this patient population. We assume that treatment with this new combination of CAR + ELO + Dex will produce at least as good responses as the most efficient regimens so far used in this clinical situation, and there will be a substantial proportion of CR responses with MRD-negativity which can be regarded as an indicator of high-level treatment efficacy and which gives a good basis for comparisons of treatment efficacy between different study regimens in future.

The target population of the study is the patients who have relapsed or progressed after 1 to 3 prior treatment lines in which PI (bortezomib and/or ixazomib) and/or lenalidomide have

Helsinki University Hospital Comprehensive Cancer Center Hematology
Clinical study protocol NMSG#24/15

been included. The primary endpoint is overall response rate (ORR) while the secondary endpoints include complete remission (CR), duration of response, assessment of the depth (quality) of CR with MRD measurement by flow cytometry, estimation of PFS and time to next treatment, and evaluation of adverse events and safety.

The cycle length is 28 days.

The ELO dose is 10 mg/kg in all cycles.

CAR dose is initially (Cycle 1, day 1) 20 mg/m² weekly after which it will be increased to 56 mg/m² weekly in the first 5 patients in the first two cycles. If no safety problems occur the dose is increased to 70 mg/m² weekly for the rest of the study, and the patients after the first 5 patients will receive this dose right after the initial weekly dose of 20 mg/m²

Dexamethasone dose is 40 mg weekly throughout the study.

Drug administration schedule:

Cycles 1-2

CAR and ELO are administrated at weekly intervals on cycle days 1, 8 and 15.

Dexamethasone will be given on days 1, 8, 15 and 22.

Cycles 3-8

CAR will be administered similarly as in cycles 1-2.

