ELO will be given on cycle days 1 and 15.

Dexamethasone as in cycles 1-2.

Cycles 9 -

CAR, ELO and Dex will be given on days 1 and 15 from cycle 9 until relapse or progression or excess toxicity.

Duration of Study:

Expected duration of treatment:

- patient recruitment 24 months
- primary endpoint (ORR) together with the relevant secondary endpoints will be assessed after the minimum follow-up of one year has been reached with the last included patient
- to assess PFS and TTNT all patients will be followed until 4 years after first dose

Helsinki University Hospital Comprehensive Cancer Center Hematology
Clinical study protocol NMSG#24/15

LIST OF ABBREVIATIONS AND GLOSSARY OF TERMS

Common abbreviations used in oncology protocols are provided below. Program-specific or protocol-specific abbreviations must be added to this list, and unnecessary abbreviations removed, as applicable. Abbreviations that are retained should not be changed.

Abbreviation	Term
AE	adverse event
AFOS	alkaline phosphatase
ALT, ALAT	alanine aminotransferase
ANC	absolute neutrophil count
API	active pharmaceutical ingredient
ASCO	American Society of Clinical Oncology
ASCT	Autologous stem cell transplantation
ASO-RQ	Allele specific oligonucleotide real-time quantification
AST	aspartate aminotransferase
AUC	area under the plasma concentration versus time curve
AUC _{24 hr}	area under the plasma concentration versus time curve from zero to 24 hours
AUC _{inf}	area under the plasma concentration versus time curve from zero to infinity
AUC _τ	area under the plasma concentration versus time curve from zero to next dose
BID	bis in die; twice a day
BM	bone marrow
BSA	body surface area
BUN	blood urea nitrogen
BZM	Bortezomib
CBC	complete blood count
CL	clearance, IV dosing
CL _p	plasma clearance
CL _{Total}	total clearance
C _{max}	single-dose maximum (peak) concentration
CNS	central nervous system
CR	complete remission
CrCl	Creatinine Clearance
CRO	Clinical trial research organization
CRP	C-reactive protein
CT	computed tomography

Helsinki University Hospital Comprehensive Cancer Center Hematology
Clinical study protocol NMSG#24/15

Abbreviation	Term
CY	Cyclophosphamide
CYP	cytochrome P ₄₅₀
DDI	drug-drug interaction
DLT	dose-limiting toxicity
DME	drug metabolizing enzymes
DNA	deoxyribonucleic acid
DSRT	Drug sensitivity and resistance testing
ECG	Electrocardiogram
ECOG	Eastern Cooperative Oncology Group
eCRF	electronic case report form
ELISA	enzyme-linked immunosorbent assay

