TTNT	Time to next treatment
UK	United Kingdom
ULN	upper limit of the normal range
US	United States
VGPR	Very good partial remission
VTE	Venous thromboembolism
WBC	white blood cell
WHO	World Health Organization

[figure not shown]
Helsinki University Hospital Comprehensive Cancer Center Hematology
Clinical study protocol NMSG#24/15

Table 1. Schedule of study investigations

	Screening	Cycles 1- until end of study, D1 (lab within 5 days before)	Cycles 1-8, D8 D15, D22* (lab within 3 days)	Cycles 1-8 D15	Cycles 9-, D15 until end of study (lab in 3days)	End of study
Medical history	X					
Physical examination + neurool.evaluation	X	X	X**			X
Vital signs	X	X	X*		X	X
Hematology	X	X				X
Immunochemistry	X	X				X
Blood chemistry	X	X				X
Pvk+neut+tromb, K,Na,krea,alat, afos,bil (safety lab*)			X*		X	
Safety assessment, AEs	X	X	X*		X	X
BM aspiration+ 8-color EuroFlow	X		X (when VGPR has achieved, repeated if VGPR/CR and after 1 year if VGPR/CR)			
Bm-MM-FISH	X					
Bone imaging	X					
ECG (a)	X					
Thorax x-ray	X					
Cardiac ECHO	X					
Biobank	X			In CR and at relapse		
Samples to FIMM in Finland	Finland			Bm + blood at relapse		
Pregnancy test (b)	X	X (b)				
Quality of Life		X		X		X

a) ECG in C1-2, D1, thereafter if clinically needed. b) Pregnancy testing must be performed at the beginning of each 28-day cycle and at the end of study visit, applying to women of childbearing potential. * Vital signs not needed on D22 and after C2 Safety lab and AEs on D22 if clinically needed. ** Physical examination if needed due to clinical symptoms.

Table 2. Study schema

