3.3. STUDY INSURANCE

Before the start of the study the sponsor-investigator and principal investigator of each site will ensure that adequate insurance for patients is in place covering losses due to death or injury resulting from the study, in accordance with applicable laws and regulations in each country where the trial is conducted (Finland, Sweden). Adequate insurance for investigators and study staff will be ensured. The pharmaceutical company supplying drugs used in the study must have their own liability insurance.

4. INVESTIGATIONAL PLAN Study design and duration

This is an investigator initiated, academic, non-randomized, open-label multicenter phase 2 study for patients with multiple myeloma in relapse or progression after 1 to 3 prior treatment lines and in need of therapy.

All patients will receive successive cycles of CAR + ELO + Dex according to the schedule shown in Table 2 and 6. Cycles are to be continued until progression, relapse or excess toxicity. The primary objective is to assess the overall response rate obtained with the regimen. This study will have phase 2a portion with 40 included patients to show the feasibility and safety of this design and if observed will be expanded to phase 2b portion with additional number of patients based on statistical power calculations..

4.1 Study procedures:

At registration each patient will have an unique identification number and following details will be documented:

- Name of study center and responsible investigator
- Date of birth of study patient
- Date of signed informed consent

Helsinki University Hospital Comprehensive Cancer Center Hematology
Clinical study protocol NMSG#24/15

- Date of treatment start

The study patient is considered enrolled on first day of study protocol treatment. Any study related investigations are not started before written informed consent.

- At inclusion: before the start of protocol treatment blood- and urine values within 2 weeks before study start, bone marrow samples within 4 weeks and bone imaging within 2 months
- During treatment: within 5 days before next cycle
- At progression and if patient is taken/withdrawn off protocol

All patients will be followed until 3 years after onset of the treatment protocol.

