4.2.4 DISCONTINUATION IN CASE OF INTOLERABILITY

Helsinki University Hospital Comprehensive Cancer Center Hematology
Clinical study protocol NMSG#24/15

Patients will continue study treatment with dose reduction by the protocol in case of intolerability by the investigator decision. Study patient can continue study treatment with 1-2 drug combination if one of the study drugs has to be permanently discontinued.

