5. TREATMENT

5.1 TABLE 6. STUDY DRUG ADMINISTRATION SCHEDULE

28-day cycle, carfilzomib will be infused first

Cycles 1-2			
Agent	Dose/day	Route	Days
Carfilzomib patients 1-5	20 mg/m ²	IV	1 (cycle 1)
	56 mg/m ²	IV	8, 15 (cycle 1)
patients 1-5	56 mg/m ²	IV	1, 8, 15 (cycle 2)
Elotuzumab	10 mg/kg	IV	1, 8, 15
Dexamethasone	40 mg	Oral/IV	1, 8, 15, 22

Cycles 1-2			
Agent	Dose/day	Route	Days
Carfilzomib -patients 6-40	20 mg/m ²	IV	1 (cycle 1)
	70 mg/m ²	IV	8, 15 (cycle 1)
	70 mg/m ²	IV	1, 8, 15 (cycle 2)
Elotuzumab	10 mg/kg	IV	1, 8, 15
Dexamethasone	40 mg	Oral/IV	1, 8, 15, 22

Cycles 3-8			
Agent	Dose/day	Route	Days
Carfilzomib - patients 1-40	70 mg/m ²	IV	1, 8, 15
Elotuzumab	10 mg/kg	IV	1,15
Dexamethasone	40 mg	Oral/IV	1, 8, 15, 22

Cycles 9 – until relapse or progression			
Agent	Dose/day	Route	Days
Carfilzomib - patients 1-40	70 mg/m ²	IV	1, 15
Elotuzumab	10 mg/kg	IV	1,15
Dexamethasone	40 mg	Oral/IV	1,15

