9.2 STATISTICAL AND EFFICACY ANALYSES

Statistical analyses will be performed on intention-to-treat and on per-protocol-treated principle. Patients who have been included in the study but been withdrawn before any study drug administration are not included in analyses. Safety and efficacy analyses will be done for all patients who have received at least a single dose of study drug. Any spurious data will be abandoned. Missing

Helsinki University Hospital Comprehensive Cancer Center Hematology
Clinical study protocol NMSG#24/15

data will be handling as missing data not with replacing it with a median parameter number.

Efficacy analyses will be done using International Myeloma Working Group response criteria (Appendix 5). Response will be assessed before each cycle. Progression will be assessed using IMWG criteria for progressive disease.

For classification the adverse events NCI CTCAE version 4.0 will be used. Threshold for safety of this CAR-ELO-Dex combination is considered to be less than 70% of grade ≥ 3 non-hematological adverse events.

Efficacy, safety and QoL analysis will be performed when last patient in has been treated for two years in the study. Kaplan-Meier method will be used to estimate the time to event analyses. The PFS, TTNT and duration of response will be calculated from the start of the first dose of study drug combination.

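### Section 5.3 orders 40 mg dexamethasone in every week without elotuzumab, with no cycle limit; from cycle 9 this contradicts Table 6, which gives days 1 and 15 only

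*Protocol*

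**What the plan says.** Section 4 of the protocol names the governing schedule: "All patients will receive successive cycles of CAR + ELO + Dex according to the schedule shown in Table 2 and 6".

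In section 5.1, Table 6 gives dexamethasone 40 mg on days 1, 8, 15 and 22 in cycles 1-8. In its last block, headed "Cycles 9 – until relapse or progression", carfilzomib, elotuzumab and dexamethasone are each given on days 1 and 15. The synopsis schedule agrees: "CAR, ELO and Dex will be given on days 1 and 15 from cycle 9 until relapse or progression or excess toxicity". Table 1 fits this: for the later cycles it has a day 1 column and one headed "Cycles 9-, D15 until end of study (lab in 3days)", and nothing for days 8 or 22.

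Two sentences say otherwise:

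- Section 5.3, under dexamethasone: "On weeks without elotuzumab, administer the weekly dose of 40 mg dexamethasone orally on day 1, 8, 15, and 22", with a window of -1 to +3 days and no cycle range.
- Synopsis, Overview of Study Design: "Dexamethasone dose is 40 mg weekly throughout the study".

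Section 4.2.4 also bears on this: "Study patient can continue study treatment with 1-2 drug combination if one of the study drugs has to be permanently discontinued". So some patients may be on treatment with no elotuzumab weeks at all.

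**The concern.** Section 5.3 is a treatment instruction that sites act on, not background text. From cycle 9 it and Table 6 cannot both be followed: one orders 40 mg on days 8 and 22, the other gives nothing on those days. A site that follows section 5.3 also finds support in the synopsis sentence.

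What is at stake:

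- **Exposure and safety.** Long-term steroid dose could double from cycle 9 through oral doses in weeks with no scheduled visit. Section 9.2 sets a safety threshold of less than 70% grade 3 or higher non-haematological adverse events, and its analysis takes place when the last patient has been treated for two years. Steroid exposure that differs between sites would feed into that figure.
- **Classification.** Section 9.2 says "Statistical analyses will be performed on intention-to-treat and on per-protocol-treated principle". With two schedules in force, it is unclear which patients were treated per protocol after cycle 8. Section 7.5 counts dexamethasone above the normal weekly dose as an overdose and requires overdoses to be reported as serious adverse events. The normal dose for the weeks of days 8 and 22 is 0 mg under Table 6 and 40 mg under section 5.3.

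**Working it through.** The protocol gives no cumulative dexamethasone figure to reproduce. The check compares the schedules and then does the dose arithmetic.

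**Inputs**

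- Cycle length 28 days (synopsis).
- Dexamethasone 40 mg per dosing day (Table 6). In elotuzumab weeks it is split as 28 mg oral + 12 mg IV = 40 mg (section 5.3, standard premedication).
- Dosing days from Table 6 and section 5.3.

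**Schedules for a patient still on elotuzumab**

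| Cycles | Elotuzumab days (Table 6) | Weeks without elotuzumab | Dexamethasone days, Table 6 | Dexamethasone days, section 5.3 read literally |
|---|---|---|---|---|
| 1-2 | 1, 8, 15 | day 22 | 1, 8, 15, 22 | 1, 8, 15, 22 |
| 3-8 | 1, 15 | days 8, 22 | 1, 8, 15, 22 | 1, 8, 15, 22 |
| 9 onward | 1, 15 | days 8, 22 | 1, 15 | 1, 8, 15, 22 |

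The two agree through cycle 8 and part at cycle 9. For a patient who has stopped elotuzumab but continues under section 4.2.4, every week is a week without elotuzumab. Section 5.3 then orders all four days, against two in Table 6.

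**Dose per cycle from cycle 9**

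- Table 6: 2 x 40 = 80 mg.
- Section 5.3: 4 x 40 = 160 mg, twice as much.

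**Cumulative dose, assuming the patient stays on full-dose treatment and section 5.3 is followed in every cycle**

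- 13 cycles (13 x 28 = 364 days, about one year): Table 6 gives 8 x 160 + 5 x 80 = 1,680 mg; section 5.3 gives 13 x 160 = 2,080 mg. Difference 400 mg; 400 / 1,680 = +23.8%.
- 26 cycles (26 x 28 = 728 days, about two years, the treatment time named in section 9.2): Table 6 gives 8 x 160 + 18 x 80 = 2,720 mg; section 5.3 gives 26 x 160 = 4,160 mg. Difference 1,440 mg; 1,440 / 2,720 = +52.9%.

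**Timing.** Cycle 9 day 1 is study day 8 x 28 + 1 = 225, about 7.4 months after the first dose.

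**The case against.** The strongest defence is that section 5.3 regulates route, not schedule. The sentence stands among the elotuzumab premedication rules and is paired with one on splitting the dose between oral and IV in elotuzumab weeks. On that reading the pair only says how to give a dose scheduled elsewhere. The day list supports this: for a patient on elotuzumab, days 1 and 15 are never weeks without it, so the list is generic and has to be read against Table 6 in any case. The synopsis sentence can likewise be read as stating a dose level, since the cycle-by-cycle schedule follows directly and ends with days 1 and 15. Section 4 settles which schedule governs.

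Part of this stands. The intended schedule can be inferred, and many sites may follow Table 6. Extra oral doses would appear in the patient's medication diary (section 5.5.1). Unsupervised oral doses are not unique to cycle 9 onward, because after cycle 2 day 22 already calls for safety laboratory tests and adverse event checks only if clinically needed. Section 9.2 does not tie per-protocol status to dexamethasone doses, so that consequence is possible rather than shown.

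It does not remove the conflict. Section 5.3 tells sites to administer the dose, names days 8 and 22, attaches a dosing window and sets no cycle limit, and the synopsis sentence backs the same reading. A dosing instruction should not depend on the reader choosing the gentler of two readings.

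**Conclusion.** The concern holds: the section 5.3 sentence is wrong as written from cycle 9, and so is the synopsis sentence. The size is 160 mg instead of 80 mg dexamethasone per cycle. The cumulative excesses of 400 mg (+24%) at 13 cycles and 1,440 mg (+53%) at 26 cycles are upper bounds. They apply only if a site follows section 5.3 over Table 6 throughout and the patient remains on full-dose treatment; the documents do not show how often that would happen.

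The matter concerns dosing and long-term safety more than the primary analysis. Cycle 9 begins on day 225, so the effect on the overall response rate is small, and neither the sample size nor the stated confidence interval changes. Table 2, to which section 4 also refers, is not reproduced in the text available and could not be checked. The point should be corrected.

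**What to change.** Limit the section 5.3 sentence and the synopsis dexamethasone sentence to cycles 1-8. State in section 5.3 that from cycle 9 dexamethasone 40 mg is given only on days 1 and 15 as in Table 6, with no dose on days 8 and 22, and that this also applies to patients who have stopped elotuzumab and continue on the other drugs.

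As a tidy-up, restrict the synopsis statement that carfilzomib 70 mg/m² is given weekly for the remainder of the study to cycles 1-8, since Table 6 gives it on days 1 and 15 from cycle 9.

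The cost is a short wording amendment and a memo to sites. Design, sample size and visits do not change.

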5.5.1 STUDY DRUG PACKAGING AND LABELING AND ORDERING

Carfilzomib

Study drug carfilzomib will be delivered free of charge from Amgen covered with final study label on packages based on subscriptions of each study site. Study sites will fill drug medication diary during protocol treatment to document the doses.

Elotuzumab

Study drug elotuzumab will be delivered free of charge from BMS covered with final study label on packages based on subscriptions of each study site. Study sites will fill drug medication diary during protocol treatment to document the doses.

Amgen and BMS will supply study drugs free of charge for the duration of this trial and dosage will be administered by the study protocol. The drugs will be sent

Helsinki University Hospital Comprehensive Cancer Center Hematology
Clinical study protocol NMSG#24/15
as labelled for study drugs to each study site. No distribution will take place
before required documentation is in place.

Dexamethasone

Dexamethasone 40 mg will be taken orally and intravenously by the specified premedication. Oral dose will be taken with the morning breakfast. This drug will be reimbursed as routine medication. Patients will fill drug medication diary during protocol treatment to document their doses.

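### From cycle 9, the dexamethasone rule in section 5.3 adds day 8 and day 22 doses that Table 6 does not give: 160 mg against 80 mg per 28-day cycle

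*Protocol*

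**What the plan says.** Two sets of text set the dexamethasone days.

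- **The schedule.** Section 4 (Investigational plan) states: "All patients will receive successive cycles of CAR + ELO + Dex according to the schedule shown in Table 2 and 6". Table 2 is not shown in the copy reviewed. Table 6 (section 5.1) has a separate block headed "Cycles 9 – until relapse or progression", in which elotuzumab and dexamethasone 40 mg are both listed on days 1 and 15. The Overview of Study Design agrees: "CAR, ELO and Dex will be given on days 1 and 15 from cycle 9 until relapse or progression or excess toxicity".
- **The administration rule.** The dexamethasone paragraph of section 5.3 states: "On weeks without elotuzumab, administer the weekly dose of 40 mg dexamethasone orally on day 1, 8, 15, and 22", with a window of -1 to +3 days. In weeks with an elotuzumab infusion, the dose is split into 28 mg oral and 12 mg intravenous. Nothing in section 5.3 or elsewhere in the protocol confines this rule to cycles 1 to 8.

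The overview also has a general dose line: "Dexamethasone dose is 40 mg weekly throughout the study".

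**The concern.** Section 5.3 is an operative instruction for a study drug. It says to administer, and it names the days and a window. From cycle 9 its days 8 and 22 are exactly the weeks without elotuzumab, so a site that works from section 5.3 gives two doses per cycle that the schedule omits. Treatment in this phase continues until progression or excess toxicity.

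Three features make the slip easier to make or harder to detect:

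- The extra doses would be oral and recorded by the patient: "Patients will fill drug medication diary during protocol treatment to document their doses". After cycle 8, Table 1 has only a day 1 column and one headed "Cycles 9-, D15 until end of study", so no visit is scheduled on day 8 or day 22.
- Section 4.2.4 says: "Study patient can continue study treatment with 1-2 drug combination if one of the study drugs has to be permanently discontinued". If elotuzumab is the drug stopped, every week is a week without elotuzumab, and section 5.3 reads as all four days in every later cycle.
- Section 7.5 counts dexamethasone above the normal weekly dose as an overdose. With two schedules in the protocol, it is unclear whether a day 8 dose in, say, cycle 10 is compliant, a deviation or a possible overdose.

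Section 1.4.3 lists hyperglycemia and decreased resistance to infection among the effects of dexamethasone, so the added exposure bears on safety.

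**Working it through.** The protocol states no dexamethasone total per cycle, so there is no figure of its own to reproduce. The check is to apply both rules to each phase and compare.

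**Inputs.** Cycle length 28 days (overview). Elotuzumab and dexamethasone days from Table 6. From section 5.3: 28 mg oral + 12 mg intravenous = 40 mg in a week with elotuzumab, and 40 mg oral in a week without.

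**Formulas.** Section 5.3 total = (weeks with elotuzumab × (28 + 12)) + (weeks without × 40), over days 1, 8, 15 and 22. Table 6 total = 40 × number of dexamethasone days listed.

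| Cycles | Elotuzumab days | Weeks without elotuzumab | Dexamethasone days, Table 6 | Section 5.3 total | Table 6 total |
|---|---|---|---|---|---|
| 1-2 | 1, 8, 15 | day 22 | 1, 8, 15, 22 | 3 × 40 + 1 × 40 = 160 mg | 4 × 40 = 160 mg |
| 3-8 | 1, 15 | days 8, 22 | 1, 8, 15, 22 | 2 × 40 + 2 × 40 = 160 mg | 4 × 40 = 160 mg |
| 9 onward | 1, 15 | days 8, 22 | 1, 15 | 2 × 40 + 2 × 40 = 160 mg | 2 × 40 = 80 mg |

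The rules agree through cycle 8 and part only at cycle 9. The gap is 160 - 80 = 80 mg per cycle, a factor of 2, and it comes entirely from days 8 and 22. This pattern fits a rule written for the weekly phase and never limited to it.

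**Sensitivity to premedication (Table 11).** After a prior grade 2 infusion reaction, an elotuzumab day carries 28 + 14 = 42 mg. The cycle 9 totals become 2 × 42 + 80 = 164 mg against 2 × 42 = 84 mg. After a grade 3 or recurrent grade 2 reaction it carries 8 + 8 + 18 = 34 mg, giving 2 × 34 + 80 = 148 mg against 68 mg. The gap stays at 80 mg.

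**After correction.** If section 5.3 follows the Table 6 days, both give 2 × 40 = 80 mg per cycle from cycle 9 with the standard premedication.

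**The case against.** The strongest reply is that the schedule is not really in doubt. Table 6 is the drug administration schedule, the overview repeats it for all three drugs, and section 4 sends every patient to it. Section 5.3 sits under a premedication heading and mainly explains the route: oral in weeks without elotuzumab, split in weeks with it. Its day list includes days 1 and 15, which are scheduled elotuzumab days in every cycle, so it may be only a catch-all of possible dexamethasone days. The overview's dose line may likewise be a loose label, because the same paragraph calls carfilzomib weekly for the remainder of the study although it too moves to days 1 and 15 from cycle 9.

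Much of this stands. It shows which text should give way and limits the practical risk. It does not remove the contradiction: section 5.3 names its own days and window without a cycle limit, and the overview's dose line supports the same reading. Nor is the extra dosing implausible enough for a site to dismiss at once. The once-weekly carfilzomib study described in section 1.4.2.1 kept day 8 dexamethasone from cycle 9.

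Two further objections also hold. The lack of a visit is a weaker argument for day 22 than for day 8, because the Table 1 footnote already makes day 22 safety checks optional after cycle 2. And multiplying the gap over time, for example 5 cycles × 80 = 400 mg by cycle 13 or 18 × 80 = 1440 mg by cycle 26, assumes uninterrupted treatment with every extra dose taken. These are hypothetical upper bounds.

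**Conclusion.** The inconsistency is real and should be corrected. The supported size is 80 mg of additional dexamethasone per 28-day cycle from cycle 9, twice the Table 6 amount under standard premedication, for a patient dosed by section 5.3. This rests on reading section 5.3 literally and on taking Table 6 as the intended schedule, which section 4 and the overview's cycle schedule support.

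A reader might infer that patients will in fact receive double the dose from cycle 9. The documents do not support that: Table 6 governs, and the number of patients dosed by section 5.3 is unknown and may be zero. A reader might also infer damage to the primary endpoint. Responses reached in cycles 1 to 8 are unaffected, because the two rules coincide there, and the sample size does not depend on this point.

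**What to change.** Replace the dexamethasone rule in section 5.3 with: *Give dexamethasone only on the days listed in Table 6 for that cycle. On any such day when elotuzumab is not given (not scheduled, held or permanently stopped), give 40 mg orally (-1 to +3 days); when elotuzumab is given, split the dose as below.*

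Replace the overview's dose line with: *40 mg weekly in cycles 1-8 and 40 mg on days 1 and 15 from cycle 9.*

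Referring to Table 6 is safer than listing fixed oral days. Elotuzumab can be held temporarily (section 1.4.1 stops it for grade 3 or higher liver enzyme elevation and allows later continuation), and a fixed list would leave a held day 1 or day 15 infusion ambiguous.

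The cost is a wording amendment. Under section 8.2 it needs ethics committee and regulatory approval before use, and the trial runs in Finland and Sweden. The correction adds no visits or procedures.
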